1. INTRODUCTION

1.1 Background and rationale:

Pregnant and postpartum adolescent girls and women in sub-Saharan Africa are one of the populations at highest risk of HIV acquisition.^{1,2} Among women living with HIV, acute maternal HIV infection during pregnancy and breastfeeding substantially increases risk of vertical transmission. In sub-Saharan Africa, acute maternal HIV infections account for an estimated 26% of all vertical HIV transmissions.^{3,4} While services to prevent vertical HIV transmission have expanded rapidly in the region, few prevention interventions exist for the majority of pregnant women who initially test HIV-negative.^{5,6} Although oral pre-exposure prophylaxis (PrEP) with tenofovir-based regimens has been shown to be effective across a variety of settings, effectiveness is highly dependent on adherence to the regimen, and may differ when pregnant or postpartum.⁷⁻¹⁰

Although considerable evidence has been gathered about the safety of antiretroviral drug use in HIV-infected pregnant women, evidence supporting the safety, feasibility, and acceptability of PrEP use during the antenatal and postpartum periods among HIV-uninfected women is needed.¹¹ In a recent systematic review done by our group, we found that there is no safety-related rationale for prohibiting TDF-based PrEP during pregnancy and/or breast feeding.⁵ Additionally, there is minimal penetration of tenofovir (the metabolite of TDF) into breastmilk.¹² While safety data are reassuring, more data on what is the most effective drug for pregnant and postpartum women are needed.

Pharmacokinetic (PK) data for PrEP remain limited. Intracellular tenofovir-diphosphate (TFV-DP) concentration in red blood cells, measured via dried blood spots (DBS) has been used to monitor adherence in many settings. In the IMPAACT 2009 study in Malawi, South Africa, Uganda and Zimbabwe found that TFV-DP in n=40 (n=20 pregnant and n=20 postpartum) African adolescent girls and young women (AGYW) was 31-37% lower in pregnancy than postpartum – indicating that strict adherence to PrEP is needed in pregnancy.

Our study will establish benchmarks of TFV-DP concentrations as measures of adherence following daily dosing with Tenofovir Alafenamide (TAF) compared with Tenofovir Disoproxil Fumarate (TDF) during pregnancy and postpartum. We will recruit from an ongoing observational cohort study in Cape Town, South Africa, PrEP-PP (recruitment ongoing through July, 2021; NIMH R01MH116771; PI [name] & [name]). Findings from this PK sub-study will be used to inform future PrEP in pregnancy and postpartum studies and develop benchmarks of the relative PK between TDF and TAF.

2. STUDY

Study aims. (1) To establish benchmarks of TFV-DP concentrations as measures of adherence following daily dosing with TAF vs TDF in pregnancy and again in postpartum; (2) To compare the difference of TFV-DP within TDF and TAF for pregnancy vs. postpartum, and to establish adherence benchmarks of levels of TFV-DP in breastmilk in postpartum women comparing the TAF and TDF samples.

Setting. The study will take place in urban townships in Cape Town (Gugulethu, NY1 and Vuyani) with high HIV incidence that spans the different socioeconomic, cultural, and ethnic groups in South Africa. We selected this community because of the high HIV prevalence there in pregnant and breastfeeding women, and because of the high number of mothers visiting every month for ANC and labour/delivery. Further, our team has several years' experience implementing research studies in this clinic which will facilitate the integration of the study there. Our study on PrEP in pregnancy ("PrEP-PP"; NIMH R01MH11677, NCT03826199) is one of the first studies to integrate PrEP into maternal child health care in South Africa and will provide the platform from which to recruit for the PK sub-study.

In 2019, the Gugulethu Midwife Obstetric Unit (MOU) saw over 3300 new ANC consultations per month, and 72% (n=2300) are HIV-negative. Considering our experience and patient flow, we are confident that at least 60 women/month per facility can be enrolled. Further, Drs. [name] and [name] have conducted research in the Gugulethu community for more than a decade and have substantial experience partnering with local health services. Building on this platform, we will use existing infrastructure in each clinic, including capacitating existing clinical providers, pharmacists and counsellors, to

provide PrEP care to pregnant and breastfeeding mothers. We will hire study staff to assist in the coordination, data management, and overall quality assurance of the drug provision, phlebotomy, and follow up.

COVID-19 and study implications. Our PrEP-PP study has continued during the COVID-19 lockdown in South Africa because it is considered to be an essential service. We continue to recruit over 15 women/week and have over 20 study retention visits in pregnant and postpartum women (telephonic and in person) during the COVID lockdown. We observe all University of Cape Town and Department of Health COVID-19 infection prevention and control methods.

Study population. Study counsellors will enroll consecutive eligible, consenting pregnant adolescent girls and women (16-40 years old) in antenatal care with singleton pregnancies, without recent PrEP exposure.

- We will enroll a separate cohort of women during singleton pregnancy at 24-30 weeks' gestation followed through postpartum until 6-12 weeks after delivery
- Women will be randomized to TAF vs. TDF and provided with directly observed oral PrEP for 8 weeks with weekly clinic visits and phone video directly observed therapy while pregnant and another 8 weeks of directly observed PrEP in postpartum period
- Women will serve as their own controls to compare their drug levels in pregnancy vs. postpartum periods
- The study will also allow for women who are enrolled and then lost to follow up to be re-enrolled into the study at a later time if they still comply with all inclusion criteria.

Sample Size: A target sample size of at least 15 women per group is consistent with similar studies of directly observed PrEP that estimated steady-state concentrations of TFV-DP, providing adequate precision for outcome estimates.¹³ We increased the sample size to 35 participants per group to account for potential attrition (total N=70 women). This study is not powered to assess safety or efficacy.

Inclusion Criteria:

1. ≥ 18 years old
2. confirmed HIV-negative (confirmed with a 4th generation antigen HIV test) at time of study entry
3. Attending ANC visits at Gugulethu MOU, NY1 Clinic or Vuyani Clinic
4. confirmed to be 20-30 weeks pregnant
5. without psychiatric or medical contraindications to PrEP
6. estimated creatinine clearance (CrCl) >60 mL/min
7. resides close to clinic (<10 km)
8. has a smart phone that can take video footage (with data bundle from study)
9. agrees to provide video phone footage of taking a pill a day for 8 weeks during pregnancy and again for 8 weeks in postpartum period
10. Previously lost to follow up participants who wish to be re-enrolled in the study so long as they still meet all of the above inclusion criteria.

Exclusion criteria:

Individuals not meeting the above criteria or meeting any of the following criteria will be excluded:

1. Concurrent enrolment in another HIV-1 vaccine or prevention trial
2. Currently taking PrEP or taken in last 90 days (except in cases of re-enrollment of previously lost to follow up participants)
3. History of renal disease
4. Current clinical diagnosis of hypertension
5. Exhibiting psychotic symptoms
6. Currently or history of taking an anti-psychotic medication

7. Positive Hepatitis B surface antigen (HBsAg) test on screening
8. History of bone fracture not related to trauma
9. Any other medical, psychiatric or social condition which in the opinion of the investigators would affect the ability to consent and/or participate in the study
10. Any maternal or fetal complication, obstetric or medical, detected during routine care or study procedures that requires referral of pregnant or postpartum women/infants to secondary or tertiary obstetric or medical care.

Study censorship will include:

1. Seroconversion
2. Moves away
3. Transfers out of care
4. Lost to follow up (e.g. does not return for study visit for >1 week and study staff are unable to track the participant, or she does not want to continue in the study).

Table 1. PK Maternal Screening Visit Procedures

Administrative and regulatory	
 - Obtain written informed consent - Assign participant identification number (PID)
Behavioral and counselling	
 - HIV testing and counselling and condom provision
Clinical	
 - Obtain medical records and medical history - Complete maternal physical exam - Weight, BMI and weight gain (monthly)
Laboratory - Blood	
 - Baseline and Monthly: Abbott 4th generation ab/ag test (negative test required prior to enrolment) - Baseline and postpartum: ALT, creatinine, CrCl, renal function panel - Baseline: Hepatitis B surface antigen (rapid test) (negative test required prior to enrolment) - Complete blood count (CBC) with differential and platelets
Laboratory- Breastmilk	
 - Collect breastmilk in postpartum women (see SOP for dried milk samples in appendix)
Study drug	
 - Prescribe and dispense study drug (TDF vs TAF depending on group) - Directly observe participant taking drug (day 1-7)
Rapid urine tests	
 - Done as needed to verify PrEP dosing prior to drawing blood samples.
Exit Interview	
 - Done at last study visit to ask questions around perceptions and experience of video observed PrEP dosing

Enrolment procedures:

Eligible, consenting women will receive up to R250 (~\$15) in grocery vouchers, transportation and refreshments per weekly visit for their time and effort in the study as well as transportation to the facility. All participants will also receive data bundles of 1GB at enrolment and 10GB every month thereafter for the duration thri follow up to send videos of them taking daily PrEP. During weekly visits, participants will receive minor refreshments (e.g. sandwich and cool drink).

Procedures for the informed consent process are outlined below. Throughout, trained study staff will ensure that women are aware of their right to refuse and/or withdraw from the study at any time. In addition, study staff will emphasize that all study activities are entirely separate from routine ANC and postnatal care services received and that refusal or withdrawal from the study will have no impact on their ability to access any services provided at any public-sector health facility.

Trained study counsellors will recruit n=70 women that are 20-30 weeks pregnant and NOT part of the ongoing PrEP-PP study for the PK sub-study. Participants will be screened for HIV infection; only those who test negative will be eligible to initiate once-daily FTC/TDF or FTC/TAF for PrEP. Participants must be willing to initiate and take PrEP and to take videos and send to the study for daily adherence for 8 weeks in pregnancy and again for 8 weeks postpartum. Women will be invited to participate in the study through ~2-3 months postpartum (depending on when they start the 8 week postpartum DOT). Women will be randomized into the TDF vs. TAF arm. Women will provide their own controls, providing pregnant and postpartum samples.

- **TDF Arm :** Women will receive a fixed dose combination of 200 mg emtricitabine (FTC) and 300 mg tenofovir disoproxil fumarate (TDF) administered once daily under direct observation for 8 weeks during pregnancy and again for 8 weeks in postpartum period
- **TAF Arm:** Fixed dose combination of 200 mg emtricitabine (FTC) and 25 mg tenofovir alafenamide (TAF) administered once daily under direct observation for 8 weeks during pregnancy and again for 8 weeks in postpartum period
- **At study end:** Participants in both arms will be given a 3 months supply of Tenemine (FTC200mg/TDF300mg).

Study Duration: Approximately 12 months total for this component. Analysis of PrEP (TAF vs TDF) drug levels will be completed within approximately three months after the last participant follow-up visit. The duration is shorter because we have ongoing cohort recruitment ongoing in Gugulethu, NY1 and Vuyani and can recruit 70 women who reside close to the clinic within 2-3 months.

Study procedures: Weekly (see **Table 2** for scheduled events), following PrEP initiation a maternal blood specimen will be collected via venepuncture (at home or in clinic, depending on participant's preference). This specimen will be used to create a DBS specimen to be tested at the laboratory at the University of Colorado. DBS cards will be prepared and stored following standard protocols and stored at -80°C for shipment and analysis at the end of the study with the clinical pharmacoanalytic laboratory of [name] at University of Colorado, Denver (funding proposal under separate cover).

Enrolled maternal participants can continue to take PrEP through delivery and postpartum period to prevent HIV during this time. Pregnancy and postpartum periods are associated with elevated risk for HIV acquisition. As such, the study aims to evaluate the different levels of TAF vs TDF associated with once-daily FTC/TDF regimen vs FTD/TAF regimen. Study staff will monitor and document maternal participants' daily administration of the study drug.

Only doses directly observed in-person or via video call by study staff or sent video recordings will be considered adequate documentation of the PrEP doses taken for the purposes of defining an evaluable participant (see Analytics).

These data will be used to determine the drug thresholds for understanding of TAF vs TDF adherence measures. The drug threshold corresponding to adequate adherence will be defined from the distribution of steady-state TFV-DP concentrations at antenatal vs postnatal visits.

If up to 3 PrEP doses were not directly observed, a urine test will be done to detect the presence of tenofovir metabolite in the participant's system prior to the drawing of blood samples.

We will evaluate the 'tail' (plasma and intracellular) of TFV and TFV-DP in the PrEP setting, comparing TAF to TDF and TAF and TDF levels in pregnant to postpartum women. See SOPs for dried milk spots (DMS) and dried blood spot (DBS) collection in Appendix.

- Plasma PK (TFV) – 8 samples in pregnancy, and 8 samples in postpartum (1 per week)
- PBMC (plasma)- 2 samples in pregnancy and 2 in postpartum at weeks 4 and 8 (4 PBMC samples per participant=100 samples)
- Breastmilk PK for TAF and TDF arms – Given there are no data on TAF in breastmilk, we propose to conduct a single sample of DMS matched with plasma samples and compare to TDF samples.
1 sample x 40 participants (TAF and TDF arms) =40 tests at 4 hours after peak (week 8)
- Urine tests- Tenofovir rapid tests will be done as needed to verify the presence of tenofovir metabolites in those participants who have stated that they have taken their PrEP but were not observed doing so.

Video DOT : We will provide the option of sharing videos of taking PrEP daily (live) instead of coming to the clinic, which has been used in previous studies led by [name] and team, including IMPAACT 2009. Participants will also be asked a few questions around their experience and perceptions of taking video observed PrEP doses during an exit interview at their final study visit.

Homebased collection of specimens : In light of COVID-19 lockdown and complexity of plasma collection, we will offer homebased collection of DBS and DMS to women by a nurse who will travel to their homes for collection of samples as required.

The PK Component will establish PK parameters for TFV-DP under TFV vs TAF under adequate adherence during pregnancy and postpartum. This PK study is necessary because it will allow investigators to compare levels of TFV-DP in TAF vs TDF and to compare levels needed for optimal adherence in pregnancy vs postpartum periods.

Table 2: Schedule of events of PK study

Weeks	During third trimester								During postpartum period								
	B	1	2	3	4	5	6	7	8	1	2	3	4	5	6	7	8
Informed consent process	X																
Medical history	X																
Concomitant medication	X																
Gestational age	X																
Safety bloods*	X												X				
Complete blood count (CBC) with differential and platelets, HCT	X												X				
HIV test (4 th gen)	X				X					X			X				X
Randomise to TAF vs TDF	X																
Dispense PrEP	X			X				X					X				X
Observed daily PrEP dosing via video call	X	X	X	X	X	X	X	X		X	X	X	X	X	X	X	X
Plasma PK sampling (TFV)	X	X	X	X	X	X	X	X		X	X	X	X	X	X	X	X
DBS	X	X	X	X	X	X	X	X		X	X	X	X	X	X	X	X
PBMC					X					X			X				X
Breastmilk Sampling [^]																	X

*Creatinine, HepBSag, ALT, renal function panel (baseline and postpartum, 2 time points),

[^] For both TAF and TDF arms

ANALYTICS

Primary Objective: To establish benchmarks of TFV-DP concentrations following daily dosing with TAF vs TDF in pregnancy and again in postpartum

Secondary Objectives: To compare the difference with TFV-DP with TDF and TAF for pregnancy against postpartum and to establish benchmarks of TFV-DP in breastmilk in postpartum women and compare with TDF arm.

Prior to conducting analyses, the study team, including the study Pharmacologists, will review the pattern of completeness of each participant's directly observed PrEP therapy (via video call) to ascertain if all 8 weeks were taken daily in antenatal and postnatal care to determine suitability for inclusion in the analysis. In each of the groups (TDF vs TAF in antenatal and postpartum groups), the distributions of steady state concentration (Css) defined as the TFV-DP concentration observed will be summarized.

For each group, we will plot median and interquartile range (IQR) TFV-DP concentrations for each week and fit a Loess curve and 95% confidence interval (CI) to the concentration-time data. The plateau in the concentration-time curve was assumed to represent steady-state. Tenofovir diphosphate at week 8 (steady-state) will be analyzed as median, IQR, mean, standard deviation (SD), and 95% CI in the pregnancy and postpartum groups by study arm. The Wilcoxon rank-sum test will be used to evaluate differences in the distribution of 8-week concentrations between groups. Additionally, a nonlinear mixed-effects population PK model will be fit to the TFV-DP data using a 1-compartment constant input model using Phoenix (Certara, Princeton, NJ). The model will be used to summarize PK parameters for both groups and between TDF and TAF arms.

Differences between the antenatal and postpartum group intra-individual comparison of plasma TDF concentrations will be evaluated using two sample t-tests. We will evaluate bio-equivalence in plasma TFV-DP between TAF and TDF in pregnant and postpartum women.

The PK testing laboratory will provide drug level results by study arm, comparing TAF to TDF in pregnancy and again in postpartum periods in the same women. The secondary objective is to compare the difference in TFV-DP in pregnancy against postpartum samples in the TAF vs TDF group. We will compare with reference ranges as it relates to the categorized level of adherence to use during adherence counselling sessions. The reference ranges will include approximately three adherence categories, aligned with other similar studies in the field. Finally, we will evaluate the level of TFV-DP in breastmilk in postpartum women and compare with TFV-DP in the TDF arm.

Qualitative Data:

- At the final study visit, participants will be asked to answer a few questions about their experience and perceptions of taking video observed PrEP doses.
- This will be done during a 20 minute exit interview.
- Participants will be asked to select a rating, from a scale, that best reflects their perceptions of the convenience, privacy, and ease of use the video observation process
- Participants will also be asked open ended questions about what they perceive to be barriers and facilitators of the video observation process.
- All answers will be anonymized by assigned ID numbers (PIPs)

Safety:

There are no indications that metabolism of TAF, TDF and TFV is sensitive to genetic polymorphisms. Population-based PK analyses indicated that race is not a clinically relevant covariate. Exposure of TAF/TFV was negligible in breastmilk.

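### Table 1 makes HIV testing monthly, but Table 2 places no HIV test between the pregnancy and postpartum dosing blocks, when PrEP may continue

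*Combined protocol and SAP*

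**What the plan says.** Table 1 (section 2) lists, under blood tests, "Baseline and Monthly: Abbott 4th generation ab/ag test (negative test required prior to enrolment". The table is titled for the screening visit, but it also lists items done later, such as breastmilk collection and the exit interview.

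The Study procedures text refers to Table 2 for the scheduled events. Table 2 has a baseline column, eight weekly columns headed "During third trimester" and eight weekly postpartum columns. It has no column for the time between the two blocks. Its row "HIV test (4 th gen" carries five marks.

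Study procedures also states: "Enrolled maternal participants can continue to take PrEP through delivery and postpartum period to prevent HIV during this time". The Enrolment procedures require a negative HIV test before PrEP is first started, and seroconversion is a listed censoring event. I found no other statement of when HIV is tested between the blocks.

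**The concern.** The plan gives staff two instructions that meet only inside the dosing blocks. A site working from Table 1 would keep testing monthly through delivery. A site working from Table 2 would have no visit at which to do so. Both could claim to follow the protocol.

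The interval matters because of what the plan says about it. The Introduction places pregnant and postpartum women in the region among those at highest risk of acquiring HIV, and says acute maternal infection substantially raises vertical transmission. Study procedures repeats that risk is elevated in both periods and lets women stay on PrEP between the blocks. In addition, observed postpartum dosing would begin with no scheduled test until postpartum week 4, whereas a negative result was required before the first start.

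**Working it through.** The plan states no length for this interval, so there is no figure to reproduce. The check has two steps: decide where the Table 2 marks fall, then compute the time between the tests on either side of delivery.

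**Step 1. Columns.** Taken by position in the extracted text, the five HIV marks are baseline, pregnancy week 4, and postpartum weeks 1, 4 and 8. The PBMC row has its four marks in the same columns as the last four HIV marks, and the text describes PBMC sampling as "2 samples in pregnancy and 2 in postpartum at weeks 4 and 8". On that description the third HIV mark belongs to pregnancy week 8. Two further facts point the same way: the extracted plasma, DBS and observed-dosing rows are blank at pregnancy week 8, yet the Analytics section analyses week 8 as steady state. I therefore use baseline, pregnancy weeks 4 and 8, and postpartum weeks 4 and 8.

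**Step 2. Inputs.**
- Entry, E: the inclusion criterion is "confirmed to be 20-30 weeks pregnant". Study population instead says "We will enroll a separate cohort of women during singleton pregnancy at 24-30 weeks' gestation followed through postpartum until 6-12 weeks after delivery".
- Block length: "8 weeks in pregnancy and again for 8 weeks postpartum".
- Postpartum start, s weeks after delivery: follow-up ends at most 12 weeks after delivery, so s is at most 12 − 8 = 4, and it cannot be below 0. Enrolment procedures puts the end at roughly two to three months; three months would allow s of about 5.
- Delivery, D: not in the documents. Assumed 40 weeks, with a range of 38-42.

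**Formula.** Gap = [D − (E + 8)] + s + 4. The first two terms are the time between the blocks, so the gap is that time plus 4 weeks. The formula applies when the pregnancy block ends by delivery (E + 8 ≤ D).

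| Entry (weeks) | Delivery (weeks) | s | Gap (weeks) |
|---|---|---|---|
| 20 | 40 | 4 | 12 + 4 + 4 = 20 |
| 24 | 40 | 4 | 8 + 4 + 4 = 16 |
| 28 (assumed start of third trimester) | 40 | 4 | 4 + 4 + 4 = 12 |
| 25 (middle of 20-30) | 40 | 2 | 7 + 2 + 4 = 13 |
| 30 | 40 | 0 | 2 + 0 + 4 = 6 |
| 30 | 38 | 0 | 0 + 0 + 4 = 4 |
| 20 | 42 | 4 | 14 + 4 + 4 = 22 |

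Taking s = 5 adds one week to each maximum. The gap stays at about a month only when the pregnancy block ends at delivery and the postpartum block starts at once.

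**Sensitivity to the columns.** With the marks by position, the gap runs from pregnancy week 4 to postpartum week 1: [D − (E + 4)] + s + 1. At D = 40 this is 6 + 0 + 1 = 7 to 16 + 4 + 1 = 21 weeks, one week more than the preferred reading. Neither reading places a test between the blocks.

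**The case against.** The best reply is that Table 2 depicts only the two dosing blocks, for every procedure, so a missing column is not a decision against testing. Table 1 is not confined to screening, and its monthly rule may be meant to cover the interval. This stands in part. The documents do not show that the plan intends to leave women untested, and they do not contradict each other at any named visit. But the intended rule has no place in the schedule that staff are told to use, and that is enough to need reconciling.

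Three stronger inferences are tempting and are not supported.

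- **Table 2 departs from monthly testing throughout.** On the reading that matches the PBMC text, testing within the blocks is about four-weekly and agrees with Table 1, apart from the absence of a mark at the start of the postpartum block.
- **Women go up to 21 weeks untested as a matter of fact.** That figure needs the by-position columns, which are probably an extraction artefact and not an error in the plan. It also needs a delivery week the documents do not give, and entry at 20 weeks, which conflicts with the 24-30 weeks stated elsewhere and sits poorly with the third-trimester heading of Table 2.
- **Late-detected infections would distort the PK results.** Tests are scheduled at postpartum weeks 4 and 8, DBS are analysed at the end of the study, and seroconversion already leads to censoring. An infection acquired in the interval could be found and the woman's samples handled before analysis. With 70 women, few such cases are likely. A rule for the censoring date would be tidy, but it is a separate and minor matter.

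**Conclusion.** The point holds as an unscheduled interval that must be reconciled. Table 1 says monthly, the operative schedule shows no HIV test between the blocks on either column reading, and PrEP may continue during that time.

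If sites follow Table 2, the interval between tests is about 6 to 20 weeks with delivery at 40 weeks, entry at 20-30 weeks and a postpartum start 0-4 weeks after delivery. It is about 6 to 16 weeks with entry at 24-30 weeks. The floor is 4 weeks, reached with entry at 30 weeks, delivery at 38 weeks and an immediate postpartum start, so not every woman exceeds a monthly interval. In most other combinations the interval is well over a month. The exact length depends on the assumed delivery week and on which entry window applies; the absence of a scheduled test does not. The weight of the point is participant safety and a schedule that sites can carry out consistently.

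**What to change.** Reconcile Table 1 and Table 2 so that one stated HIV-testing frequency governs. Show in Table 2, by an added column or a footnote, what applies between the pregnancy and postpartum blocks and at the start of postpartum dosing. Which frequency governs is for the investigators to decide. When the table is revised, check that the marks sit in the intended columns and that one entry window is used throughout.

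The cost is one table row or footnote and a sentence of text. If the monthly statement governs, the added tests are ones Table 1 already promises. At four-week spacing, a 6-week gap would hold one (at 4 weeks), a 20-week gap four (at 4, 8, 12 and 16 weeks), and a 4-week gap none.

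### The pregnancy-versus-postpartum week-8 contrast in dried-blood-spot TFV-DP does not allow for unequal starting levels, so it can make pregnancy look too low if the half-life is long and many women continue PrEP between periods

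*Combined protocol and SAP*

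**What the plan says.** All references are to the combined protocol and SAP, section 2.

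- **Start of the pregnancy period.** The exclusion criteria rule out "Currently taking PrEP or taken in last 90 days (except in cases of re-enrollment of previously lost to follow up participants". First-time enrollees are therefore PrEP-free for 90 days; re-enrolled women are exempt.
- **Between the periods.** Study procedures states: "Enrolled maternal participants can continue to take PrEP through delivery and postpartum period to prevent HIV during this time". It requires neither a washout nor continuation. The same paragraph says that staff will track and record daily dosing, without limiting this to the two 8-week periods.
- **Start of the postpartum period.** Study population has women "followed through postpartum until 6-12 weeks after delivery". Enrolment procedures gives about 2-3 months, "depending on when they start the 8 week postpartum DOT".
- **Analysis.** The Analytics section has the team review observed dosing "to ascertain if all 8 weeks were taken daily in antenatal and postnatal care to determine suitability for inclusion in the analysis". It will "fit a Loess curve and 95% confidence interval (CI) to the concentration-time data", and adds: "The plateau in the concentration-time curve was assumed to represent steady-state". TFV-DP at week 8, labelled steady state, is summarised by period and arm. A rank-sum test compares 8-week levels between groups. A one-compartment population PK model with constant input is also fitted; its starting amount is not stated.

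**The concern.** Each woman is her own control, so the pregnancy-postpartum contrast is fair only if week 8 means the same thing in both periods. Two effects need to be kept apart. First, if TFV-DP is cleared slowly, eight weeks from zero falls short of steady state (Css) and pregnancy is under-read. Second, a woman who carries drug into the postpartum period gets nearer to Css by postpartum week 8. The first effect exists without the second; together they make the two periods unequal.

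The resulting error runs in the same direction as the finding the study has reason to expect, since Background and rationale cites levels 31-37% lower in pregnancy. A reader of the raw week-8 values could not separate the artefact from physiology. The contrast is a named secondary objective, and Study procedures derives adherence thresholds from steady-state levels at antenatal and postnatal visits.

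**Working it through.** **Inputs from the documents.** Each observed period is 8 weeks (56 days). Entry is at 20-30 weeks (inclusion criteria; Study population says 24-30). Follow-up ends 6-12 weeks after delivery.

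**Assumptions.** The documents give no half-life and no share of women who continue, so there is no plan figure to reproduce. I take half-lives h of 5, 10, 17 and 25 days, the same in both periods, first-order accumulation, and delivery at 40 weeks.

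**Gap between periods.** An 8-week postpartum course ending by week 12 starts at 0-4 weeks. Gap = 40 − (entry + 8) + (0 to 4), which is 2-16 weeks for entry at 20-30 weeks and 2-12 weeks for entry at 24-30.

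**Formulas.** k = ln 2 / h; levels are fractions of Css.
- Pregnancy week 8 from zero: P = 1 − exp(−56k).
- Postpartum start after a stop of g weeks: f = P·exp(−7kg).
- Postpartum week 8 after a stop: S = 1 − (1 − f)·exp(−56k).
- PrEP continued through an 8-week gap (56 + 56 + 56 = 168 days): C = 1 − exp(−168k).
- Apparent pregnancy reduction: 1 − P/(postpartum week 8). In a mixed cohort with share w continuing: 1 − P/[wC + (1 − w)S].

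The zero start is reasonable for first-time enrollees: after 90 days off drug the residual, 2^(−90/h), is 0.0020, 0.0255 and 0.0825 of Css at 10, 17 and 25 days.

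**Results with no true difference**

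| Half-life (days) | 5 | 10 | 17 | 25 |
|---|---|---|---|---|
| Pregnancy week 8, % of Css | 100.0 | 97.9 | 89.8 | 78.8 |
| Postpartum week 8, 8-week stop | 100.0 | 98.0 | 90.7 | 82.4 |
| Postpartum week 8, continued through 8-week gap | 100.0 | 100.0 | 99.9 | 99.1 |
| Apparent reduction: full carry-over (upper bound) | 0.0% | 2.1% | 10.2% | 21.2% |
| 25 / 50 / 75% continue, 8-week gap | <0.1% | 0.6 / 1.1 / 1.6% | 3.5 / 5.8 / 8.0% | 8.9 / 13.1 / 16.9% |
| All stop for 2 weeks | 0.0% | 0.8% | 5.4% | 12.6% |
| All stop for 8 weeks | 0.0% | <0.1% | 1.0% | 4.3% |
| All stop for 16 weeks | 0.0% | 0.0% | 0.1% | 0.9% |

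Example at 17 days with half continuing: 1 − 0.898/(0.5 × 0.999 + 0.5 × 0.907) = 5.8%.

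**With a true reduction r of 31-37%.** Pregnancy week 8 is (1 − r)P on the postpartum Css scale. If postpartum dosing starts at the pregnancy Css, postpartum week 8 is 1 − r·exp(−56k). At 17 days and r = 0.31 this reads 1 − (0.69 × 0.898)/(1 − 0.31 × 0.102) = 36.0%. Over r = 31-37% the readings are 32-38% (10 days), 36-41% (17 days) and 42-46% (25 days).

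**If the PK model were fitted from zero in each period.** Fitting A(1 − exp(−kt)) to eight noise-free weekly postpartum points with a true start at 25% of Css gives a Css that is 0.6%, 3.2%, 9.4% or 17.5% too low at the four half-lives. Adding an estimated starting level to such fits returned the true Css and half-life at every half-life and starting level tried (7-25 days).

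**The case against.** **Materiality rests on an undocumented half-life.** This stands. At 10 days or less the error is at most 2.1%, and after an 8-week stop in all women it is 1.0% at 17 days. If week 8 truly is steady state, as the plan assumes, the starting level does not matter.

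**The plan already has partial safeguards.** Staff document daily dosing, and weekly plots with a Loess curve would show a raised early postpartum curve and help reveal a missing plateau. A reader might infer that dosing between periods goes unrecorded, but the documentation sentence is general and may well cover it. What is missing is a stated use of that record: showing an unequal start does not adjust the contrast for it.

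**The scope is narrow.** This also stands. Carry-over brings raw postpartum week-8 benchmarks nearer to Css. It reaches pregnancy benchmarks only through re-enrolled women. The plasma t-test is outside the point, and the TAF-TDF comparison within pregnancy is largely unaffected because both arms start alike.

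**The wording leaves room.** The rank-sum test is described as between groups and may include the arm comparison. The model is not said to start from zero, so the fitted-model error above describes a choice the plan has not made.

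**A stronger reading is tempting.** One might infer that a true 31-37% reduction would read 38-43% at 17 days or 46-50% at 25 days, from 1 − (1 − r)P. Those are ceilings: they assume the postpartum period starts already at the postpartum Css. If pregnancy lowers levels, a woman who dosed throughout enters nearer the pregnancy Css, and a start 0-4 weeks after delivery leaves little time to rise.

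**Conclusion.** The point holds as a limited, inexpensive improvement to the analysis of the secondary DBS TFV-DP contrast. The unequal starting levels follow from the text, and no stated analysis adjusts for them. Raw week-8 values can make pregnancy look too low, by an amount that depends on the half-life and the share of women who continue. Under the stated assumptions the error is negligible at 5-10 days. At 17 days it is 3.5-8.0%, and at 25 days 8.9-16.9%, when 25-75% continue through an 8-week gap; the upper bounds are 10.2% and 21.2%.

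A reader might infer that the artefact could account for the whole 31-37% difference cited in the background. It could not: even the upper bound at the longest assumed half-life falls short of 31%. Nor do the documents support a claim that the postpartum benchmarks are spoiled. Confidence is medium, because neither deciding quantity is in the documents.

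**What to change.** 1. Confirm that the documentation of daily dosing in Study procedures covers the interval between the two periods (dates continued or stopped), and state that the record is used in the analysis.
2. Fit the planned population PK model with the full dose history and an estimated starting amount for each period, including for re-enrolled women.
3. Keep the observed week-8 summaries, report model-derived Css beside them, and add one sensitivity analysis of the within-woman contrast by PrEP continuation (yes or no) and gap length.

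The cost is SAP wording, a short dosing record and some modelling work. The weekly DBS samples already planned support it, so no extra sample is needed. If the half-life proves short, the sensitivity analysis will show that little changes. No change to PrEP access is proposed. The 20-30 and 24-30 week entry passages must be reconciled as a separate matter; here they only set the range of gaps.
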